#### **4.3.2 Time to treatment failure**

##### **4.3.2.1 Methods of assessment**

The number of days from start of treatment after randomization to treatment failure or, in case of no treatment failure, from start of treatment after randomization to last visit in the study.

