During the 5-year prolongation, all subjects will visit the hospital after 6, 7, 8, 9 and 10 years for assessments. At 5.5, 6.5, 7.5, 8.5 and 9.5 the subjects will have a telephone visit (hospital visit optional). The hospital visit should be done by the investigator and the telephone should preferably be done the investigator.

Randomized subjects who have discontinued but not withdrawn their informed consent will be followed-up by a phone call from the investigators at 5 and 10 years after randomization. This will also be applicable for subjects who discontinue during the prolonged period. The follow-up phone call consists of questions about the subject's surgery related to GERD, present medical treatment of GERD and present symptom load. For more information see Appendix P to the amendment

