**Subjects untreated with PPI prior to study start will (if possible):**

- (i) start the run-in period with the “investigational week” at visit 1. In such cases an endoscopy with biopsy sampling will be made at visit 1. If insufficient biopsies have been taken at visit 1 then another endoscopy with biopsy sampling will be done at visit 3. In cases of mucosal breaks classified as LA grade C or D at visit 1 or 3 a new endoscopy must be performed at visit 4 prior to randomization. Furthermore, laboratory measurements, 24 hr pH metry, manometry and SAP will be made. If these assessments can be made within 2 weeks from visit 1 then visit 2 and 3 can be left out. The study drug (esomeprazole 40 mg o.d.) will then be dispensed and the subject will continue the run-in period. If the time between first endoscopy (visit 1) and the 24 hour pH metry is more than 2 weeks, the study drug must be dispensed at visit 1 and the subject will follow the same routine as the **treated subject (i)**.

10-year study period

If reflux esophagitis LA grade C or D is found at visit 3, a new endoscopy must be done at visit 4 prior to randomization.

- Subjects will be randomized to either medical treatment or surgery at visit 4. Medical treatment is 20 mg o.d. (start dose) and can be adjusted, but is not to exceed 40 mg daily. Surgery must be performed within 3 months after randomization. The subject is allowed to be treated with esomeprazole 20 mg o.d. and can be adjusted, but is not to exceed 40 mg daily whilst awaiting the surgery. Visit 5 and 6 will only be attended by subjects randomized to surgery.
- Endoscopy with biopsy sampling will be performed at visit 8, 12, 16, 33 and 39. A 24 hour pH metry and SAP will be performed at visit 7 and 16. Endoscopy will be performed at extra visits in case of symptomatic relapse or early discontinuation. A 24 hr pH metry and SAP should be performed in case of dose adjustments (prior to).
- Symptoms will be assessed at each visit except at visit 5 and the telephone visits (visit 30, 32, 34, 36, 38). Laboratory screen will be done at visit 8, 12, 16, 33 and 39 and at early discontinuation visits.
- Patient reported outcomes (PRO) will be assessed by QOLRAD and GSRS at visits 4, 8, 10, 12, 14, 16, 31, 33, 35, 37 and 39 and at early discontinuation visits.
- Body weight will be assessed at visits 4, 8, 12, 16, 33, 39 and at extra visits and at early discontinuation visits.

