- 10 Only for subjects with RE LA grade C or D at visits 1 or 3.
- 11 Only body weight
- 12 30 days after visit 5 (surgery)
- 13 Only for subjects in the surgical arm receiving esomeprazole
- 14 Only for subjects in the medical arm
- 15 In case of administration of healing dose (esomeprazole 40 mg o.d.)
- 16 In case of dose adjustment
- 17 In case of premature discontinuation after randomization (visit 4)

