### **3.4.2 Doses and treatment regimens**

The medication arm of the study design includes the following:

- esomeprazole
- oral administration
- the start dose is 20 mg once daily and may be adjusted not to exceed 40 mg total daily dose and be swallowed together with a glass of water.

The surgical arm of the study design includes the following:

The surgical procedure is laparoscopic fundoplication. The surgical procedure to be used is laparoscopic total fundoplication and reconstruction of the hiatus. A per-operative record should be filled in and sent by the monitor to AstraZeneca R&D Mölndal for datahandling. The procedure should be done by or supervised by an experienced surgeon. Surgery should be performed within three months of randomization. The subject is allowed to be treated with esomeprazole 20 mg o.d or 40 mg o.d awaiting the surgery.

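### The primary time-to-failure clock starts at an undefined start of treatment, up to 3 months after randomisation if that means the operation; the effect is probably small

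*Protocol*

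**What the plan says.** Section 4.3.2.1 of the protocol gives the primary time as "The number of days from start of treatment after randomization to treatment failure", and for subjects without failure as the time from the same origin to the last visit. Section 4.3.2.2, the place for a derivation, adds none.

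Randomisation has a fixed date: "Subjects will be randomized to either medical treatment or surgery at visit 4". The operation does not. Section 3.1 (10-year study period) says "Surgery must be performed within 3 months after randomization", and Section 3.4.2 repeats it: "Surgery should be performed within three months of randomization". On the interval between, Section 3.4.2 says "The subject is allowed to be treated with esomeprazole 20 mg o.d or 40 mg o.d awaiting the surgery"; Section 3.4.5 words this as something that should happen rather than something permitted.

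Follow-up is tied to randomisation. Table 1 sets visit 4 at month 0 and uses the same columns for both arms (visit 7 at 6 months, visit 16 at 60 months); only visit 6 is counted from the operation. Discontinued subjects are "followed-up by a phone call from the investigators at 5 and 10 years after randomization".

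The interim analyses have two origins. Section 3.1 counts from the last subject randomised in the medical arm or operated on in the surgical arm. Section 6.2.4 counts from the last subject randomised.

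Section 6.2.1 removes from the ITT set medical subjects who took no dose and surgical subjects who refuse the operation. Section 6.2.3 censors discontinuation for reasons other than treatment failure.

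**The concern.** In the medical arm, start of treatment and randomisation nearly coincide. In the surgical arm, start of treatment can mean the operation or the esomeprazole given while waiting. The interim wording in Section 3.1 points to the operation, but nothing in the endpoint definition says so.

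If it is the operation, the arms are measured from different points. A failure or withdrawal during the wait has no place on the surgical clock, while a withdrawal at the same time in the medical arm is censored with its follow-up counted. A surgical subject never operated on for a reason other than refusal (an adverse event or pregnancy, for instance, both listed in Section 3.3.5.1) stays in the ITT set with no time zero. Surgical follow-up at any scheduled visit is shorter by the length of the wait.

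At stake is whether the main comparison starts where randomisation made the groups comparable. The trial is open, so an origin left to be settled later could be chosen with outcomes in view.

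**Working it through.** **Inputs.** Success at 5 years 70% in each arm (the lower bound assumed in Section 6.1); 275 subjects per arm and precision of 8 points (Section 6.1); longest wait 3 months = 0.25 year (Sections 3.1 and 3.4.2); two-sided logrank test (Section 6.2.3). Constant hazard is an assumption, and so is a 5% level, taken from the 95% in Section 6.1.

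**The plan's own figure.** Half-width = 1.96 × √(2 × 0.70 × 0.30 / 275) = 7.66 points, or 8.02 with a continuity correction of 1/275. The stated 8 points is reproduced. It uses no time origin, so a change of origin does not affect it.

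**Follow-up.** With the operation as origin and a 3-month wait, a surgical subject has 60 − 3 = 57 months on the clock at visit 16, against 60 in the medical arm. At year 10 it is 120 − 3 = 117 against 120.

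**Effect on the rate.** Hazard = −ln(0.70)/5 = 0.0713 per year.
- Read at visit 16, success on the surgical clock is 0.70^(4.75/5) = 71.3%, against 70.0%: a shift of 1.26 points. For waits of 1 and 2 months the shift is 0.42 and 0.84 points.
- Read at 5 years from the operation, a surgical subject is 5.25 years from randomisation: 0.70 × (1 − exp(−0.0713 × 0.25)) = 1.24 points.
- The same offset gives 82.2% against 80.7% at 3 years (1.5 points) and 49.9% against 49.0% at 10 years (0.9 points).

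The 5-year shift is about one sixth of the planned precision (1.26/8 = 0.16).

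**Effect on the test.** In 4,000 simulated trials with no true difference, constant hazard, the operation as origin and failures during the wait left out, the logrank test rejected in 5.3% when all surgical subjects waited 3 months and in about 4.8% with waits uniform over 0 to 3 months. Counting both arms from randomisation gave 4.7%. The simulation standard error is √(0.05 × 0.95/4000) = 0.34 points, so all three are consistent with 5%.

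**The other reading.** If start of treatment is the esomeprazole given while waiting, Table 1 dispenses study drug at visit 4 without restriction by arm, so the clock starts close to randomisation in both arms. Dropping refusers then still selects on an event after randomisation in the surgical arm.

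**The case against.** The case for leaving the text alone has force. A clock from treatment start fits a population that leaves out non-starters in both arms, and Section 6.2.1 promises a statistical analysis plan in which an exact start date could be fixed. At constant hazard, each arm measured from its own start reaches 70% at 5 years, so the 1.2 to 1.3 points reflect a shifted horizon and not a biased curve. The primary analysis is a logrank test with survival curves and a median; a 5-year rate appears only in the precision statement. All of this limits the size. It does not supply the missing definition or remove the conflict over the interim origin.

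A reader might infer three stronger points that the documents do not support.

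- **A seriously inflated test in favour of surgery.** If failures are assumed to come early (Weibull shapes 0.7 and 0.5), simulated rejection is 9.0% and 32.5% with a 3-month wait for all, or 6.7% and 16.5% with uniform waits. But this needs medical failures in the first 3 months. Under Section 4.1 a medical subject starting at the Section 3.4.2 dose passes through two 8-week dose steps before failure can be declared, about 16 weeks. The 4.9 medical failures per 275 that a constant hazard puts in that window (275 × 1.77%) could not arise either. Surgical subjects, by contrast, can fail on the day of operation.
- **A nearly empty surgical tail at 5 years.** With waits uniform over 0 to 3 months and a ±2-week window (0.46 month), (0.46²/2)/(3 × 0.92) = 3.8% of surgical subjects are seen at exactly 5.0 years, against 50% of medical subjects. Table 2 gives visit 16 a ±6-week window (1.38 months), which makes it (1.38²/2)/(3 × 2.76) = 11.5%. Both figures assume that follow-up is cut at visit 16, although subjects reaching it are asked to continue. Neither the logrank test nor the median uses this fraction.
- **An ITT set of operated subjects only, with guaranteed failure-free time.** Section 6.2.1 drops those who refuse; subjects not operated on for other reasons remain.

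**Conclusion.** The point holds as a defect of definition in the primary endpoint. The origin is undefined in the surgical arm; the reading suggested by Section 3.1 departs from randomisation by up to 3 months in that arm only; and Sections 3.1 and 6.2.4 disagree on the interim origin.

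The numerical effect is probably small: about 1.2 to 1.3 points on the 5-year rate for a full 3-month wait, less for shorter waits, with logrank error near nominal. This rests on constant hazard and 70% success at 5 years. Constant hazard is a simplification, since the medical failure rule leaves roughly the first 16 weeks without failures. The direction of any remaining bias cannot be settled from the protocol. The reason to act is that the correction is cheap and closes a choice that should not stay open in an unblinded trial.

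**What to change.** - In Section 4.3.2.1, count days from randomisation (visit 4) to treatment failure, or to the last visit, in both arms for the main ITT analysis.
- In Section 6.2.1, keep all subjects randomised to surgery in that analysis, including those who refuse and those not operated on for other reasons. State how failure or withdrawal before the operation is counted. Without this, moving the origin only gives the surgical arm waiting time that is largely failure-free by selection. For symmetry, treat medical subjects who take no dose in the same way.
- Keep time from operation as a supportive analysis of operated subjects.
- Reconcile the interim timing in Sections 3.1 and 6.2.4.

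The cost is a few sentences. Randomisation and surgery both take place at scheduled visits, so no new data are needed, and the sample size does not change. The downside is a slightly longer surgical clock that includes the waiting time.

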##### **4.3.2.2 Calculation or derivation of endpoint**

Not applicable

#### **4.3.3 Histopathological changes**

##### **4.3.3.1 Methods of assessment**

Histopathological changes will be assessed by observing the biopsy specimens taken during endoscopy. The biopsy specimens will be sent to a central laboratory with courier. The Central laboratory will send all biopsies for analyses to the pathologist, . A short diagnostic report will be sent to the investigator by fax or email. In addition, the grading of the histological parameters and a full report will be sent to AstraZeneca.

In case of endoscopic suspicion of malignancy, additional biopsies, outside of this protocol should be taken and sent to the local pathology department of each hospital or institute.

Biopsy sampling, handling and logistics will be found in Appendix H.

##### **4.3.3.2 Calculation or derivation of endpoints**

Not applicable

#### **4.3.4 Endoscopic and symptomatic relapse**

##### **4.3.4.1 Methods of assessment**

The method of assessment of endoscopic recurrences will be endoscopy. The endoscopic examination of esophagus, cardiac region, stomach, and duodenum will be done in each subject. The subject should be fasting at least 12 hours prior to endoscopy. Endoscopic findings will be classified according to the Los Angeles classification grade A to D.

- |         |   |
|---------|---|
| Grade A | One (or more) mucosal break no longer than 5 mm, that does not extend between the tops of two mucosal folds                                 |
| Grade B | One (or more) mucosal break more than 5 mm, that does not extend between the tops of two mucosal folds                                      |
| Grade C | One (or more) mucosal break that is continuous between the tops of two mucosal folds but which involves less than 75% of the circumference. |

Grade D One (or more) mucosal break, which involves at least 75% of the esophageal circumference.

Biopsies will be taken in the antrum, the corpus, the cardiac region (grasping the Z-line) and esophagus. 2 biopsy specimens (3 from the Z-line) will be taken from each location (see also Section 4.3.3.1 and appendix H). The biopsies will be preserved and stored, according to local procedures for a maximum time of 15 years after the end of the study for future analysis.

The presence of a stricture and/or columnar lined esophagus (CLE) will be separately recorded and the extent of CLE assessed. Video endoscope should be used. Biopsy sampling in the esophagus may be taken with antegrade or retrograde technique and should be recorded in the CRF.

#### 4.3.4.2 Calculation or derivation of endpoint

Endoscopic relapse is defined as an endoscopic finding of LA grade C to D. Symptomatic relapse has occurred when a subject has recurrent GERD symptoms (moderate-severe, see below) over 3 consecutive days before the clinical visit.

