**Need for medical treatment for control of symptoms from reflux disease:**

In order to allow for a stringent assessment of treatment failure ask the following question:

*“Do you have sufficient control of your heartburn and acid regurgitation?”*

If the answer is **No**, continue with:

*”Do you need other regular drug treatment to control your symptoms?”*

If the answer to this question is **Yes** the subject has to be classified as a **treatment failure and will be withdrawn**.

Furthermore, the subject will also be regarded as a **treatment failure** if the following occurs;

- Post-operative - post-fundoplication complaints requiring further medical actions to control symptom burden.
- Per-operative death
- Post-operative death within 30 days after surgery
- Dysphagia requiring further treatment. In case of esophageal stenosis, one dilatation is allowed.

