#### 4.3.5 Gastrointestinal symptoms associated with GERD over time

##### 4.3.5.1 Methods of assessment

###### GERD symptoms

The method of assessment of symptoms will be a questionnaire in the CRF. At each visit, the presence of symptoms will be assessed retrospectively by the investigator in a standardized manner. The definition for each symptom is:

- heartburn a burning feeling, rising from the stomach or lower part of the chest up towards the neck
- acid regurgitation flow of sour or bitter fluid into the mouth
- dysphagia difficulties in swallowing

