#### 4.4.2.2 Recording of adverse events

SAEs and AEs causing premature discontinuation of study drug and/or study will be recorded retrospectively by the investigator in the Case Report Form at visit 2 and the following visits. If any SAE or AE causing premature discontinuation of study drug and/or study are ongoing at the subjects last visit in the study, they must be followed up after 2 to 4 weeks and thereafter as long as medically indicated. This can be done either as an extra visit to the clinic or by written or verbal contact with the subject.

Spontaneously reported SAEs and AEs causing premature discontinuation of study drug and/or study, objective findings and observations, and SAE and AEs causing premature discontinuation of study drug and/or study reported in response to the standardized question “Have you had any health problems since the previous visit?” will be recorded in the CRF. Start and stop date (or marked as ongoing), outcome, maximum intensity, seriousness, and action taken with regard to investigational product and if the AE caused subject to discontinue the study will be recorded. Maximum intensity will be rated according to the following scale:

- |              |  |
|--------------|--|
| 1 = Mild     | - awareness of sign or symptom, but easily tolerated                 |
| 2 = Moderate | - discomfort sufficient to cause interference with normal activities |
| 3 = Severe   | - incapacitating, with inability to perform normal activities        |

It is important to distinguish between serious and severe AEs. Severity is a measure of intensity whereas seriousness is defined by the criteria in Section 4.4.2.1. An AE of severe intensity need not necessarily be considered serious. For example, nausea, which persists for several hours, may be considered severe nausea, but not a SAE. On the other hand, a stroke which results in only a limited degree of disability may be considered a mild stroke but would be a SAE.

Abnormal test results from laboratory investigations or endoscopy investigations (including biopsies) that meet any criteria of an SAE must be reported in accordance with the SAE reporting procedures (see Section 4.4.2.3).

Symptoms included in the efficacy variables

- Section 4.3.5.1 GERD symptoms (i.e. heartburn, acid regurgitation, dysphagia)
- Section 4.3.5.1. other GI symptoms (i.e. epigastric pain, flatulence, bloating, ability to vomit, ability to belch, diarrhoea)

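### Dysphagia alone can count as symptomatic reflux relapse, and tables and text disagree on the extra-visit endoscopy trigger, so symptomatic and between-visit endoscopic relapse may be distorted between arms

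*Protocol*

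**What the plan says.** **Symptomatic relapse.** Section 4.3.4.2 of the protocol reads: "Symptomatic relapse has occurred when a subject has recurrent GERD symptoms (moderate-severe, see below) over 3 consecutive days before the clinical visit". The next section, 4.3.5.1, has a list headed as GERD symptoms with three entries: heartburn, acid regurgitation and "dysphagia difficulties in swallowing". Epigastric pain, flatulence, bloating and diarrhoea stand under a separate heading for other GI symptoms. Section 4.4.2.2 repeats the grouping: "GERD symptoms (i.e. heartburn, acid regurgitation, dysphagia".

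**Primary endpoint.** Sections 4.1 and 6.2.2 open the failure assessment in both arms with the question "Do you have sufficient control of your heartburn and acid regurgitation". Dysphagia is not part of it. It appears lower down, for the surgical arm only, as a failure criterion of its own: "Dysphagia requiring further treatment. In case of esophageal stenosis, one dilatation is allowed".

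**Extra-visit endoscopy.** The text of section 3.1 says "Endoscopy will be performed at extra visits in case of symptomatic relapse or early discontinuation", without restriction by arm. It also offers an endoscopy to satisfied subjects with a temporary moderate-severe episode, before the text divides by arm. For the same table cell, Table 1 footnote 15 says "In case of administration of healing dose (esomeprazole 40 mg o.d", and Table 2 footnote f says the same for the prolongation.

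**Use of the data.** Table 3 lists endoscopic and symptomatic relapse, each as point prevalence (at scheduled visits) and periodic prevalence (between them). Section 6.2.3 presents them by treatment group, endoscopic and symptomatic relapse combined as well as separately. All of this is descriptive.

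**The concern.** The relapse tables are meant to show how well each strategy controls reflux over up to ten years. Two features can make the arms differ for other reasons.

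First, the protocol itself handles dysphagia as a consequence of the operation when it defines surgical-arm failure, yet the relapse definition lets the same symptom count as reflux recurrence. A surgical subject with no heartburn and no regurgitation, but with moderate swallowing difficulty for three days, meets the definition as written.

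Second, endoscopic relapse between scheduled endoscopies can be found only if an unscheduled endoscopy is done. If the trigger is an esomeprazole dose, the chance of looking depends on the arm.

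At stake is the reading of one stated secondary objective, the point and periodic prevalence of recurrences, in an open trial of drug against surgery.

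**Working it through.** The protocol gives no figure for relapse or dysphagia. Its only design figure, in section 6.1, concerns the primary endpoint: with 275 per arm and 70% success, 1.96 × √(2 × 0.70 × 0.30 / 275) = 0.0766, which agrees with the stated 8 points. Nothing below rests on it.

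**Step 1: does dysphagia alone qualify?** The reference onward in section 4.3.4.2 leads to section 4.3.5.1, which holds both the symptom list and the severity grades. Even if it is read as pointing only to the grades, section 4.4.2.2 independently names the three GERD symptoms, dysphagia included. No passage requires heartburn or regurgitation to be present. So dysphagia alone qualifies, subject to how the undefined word recurrent is read (see the objection).

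**Step 2: possible size for symptomatic relapse.** Let r be true reflux relapse, equal in both arms, and let d be moderate-severe dysphagia, independent of r. Measured relapse = 1 − (1 − r)(1 − d). The spurious difference is (1 − r)(d surgical − d medical). All rates are assumptions.

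With r = 10%, d medical = 2%, and measured medical relapse = 1 − 0.90 × 0.98 = 11.8%:

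| d surgical | measured surgical relapse | difference (points) |
|---|---|---|
| 2% | 11.8% | 0 |
| 5% | 1 − 0.90 × 0.95 = 14.5% | 2.7 |
| 10% | 1 − 0.90 × 0.90 = 19.0% | 7.2 |
| 15% | 1 − 0.90 × 0.85 = 23.5% | 11.7 |

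At d surgical = 15%, the difference is 0.95 × 13 = 12.35 points for r = 5% and 0.80 × 13 = 10.4 points for r = 20%.

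**Step 3: who gets an extra-visit endoscopy?**
- *By the text of section 3.1:* symptomatic relapse triggers it in either arm.
- *By the table footnotes:* the healing dose triggers it. For a temporary episode, section 3.1 gives the medical arm 40 mg o.d. and the surgical arm antacids. Section 3.4.5 allows 40 mg o.d. after surgery only for ulcer or erosion. A surgical relapse managed within the study therefore does not meet the footnote.
- *At discontinuation:* treatment failure is a reason for discontinuation (section 3.3.5.1), and section 3.3.5.4 and the discontinuation columns of both tables require an endoscopy without that footnote. Surgical relapses that end in withdrawal are therefore examined under either reading.

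**Step 4: possible size for between-visit endoscopic relapse.** Assume that 20% of symptomatic relapses in both arms carry LA grade C-D, that every medical-arm relapse is examined, and that a fraction f of surgical-arm relapses is. Relapses found per 100: medical 20; surgical 20 × f, which is 0, 5, 10 or 20 for f = 0, 25%, 50% or 100%. The gap closes if the text of section 3.1 is followed. Full coverage in the medical arm is generous under the footnotes, because a subject moved from 40 mg once daily to 20 mg twice daily does not literally meet them either.

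**Step 5: what is untouched?** Endoscopies at visits 8, 12, 16, 33 and 39 are done in both arms, and endoscopic relapse is LA grade C-D in both, so endoscopic point prevalence does not depend on either issue. Relapse is not a component of treatment failure, so the log-rank analysis is unaffected.

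**The case against.** The best defence is that calling dysphagia a GERD symptom is a choice, made consistently in two sections and applied by one rule to both arms. The definition also asks for recurrent symptoms. Recurrent dysphagia is an exclusion at entry (section 3.3.4, criterion 6), so new dysphagia after surgery might be read as not recurrent. Subjects whose dysphagia needs treatment are failures and leave, so they should not add relapses visit after visit. Symptoms are recorded one by one and tabulated by visit and arm, so dysphagia can be separated later. The relapse endpoints are descriptive, and the text of section 3.1 already gives an arm-neutral endoscopy rule.

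Much of this stands and limits the point. It does not remove it. Recurrent is not defined, so the reading that excludes new dysphagia is only one of two. A uniform rule still misleads when one treatment can itself produce the symptom. Dysphagia that is moderate or severe but left untreated stays in the count. Being able to separate the symptoms helps only if the plan says that this will be done.

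Three stronger readings are tempting, and the documents do not support them:
- That no relapse endpoint is comparable between arms: scheduled endoscopies are the same in both.
- That the surgical arm would have no relapse-related endoscopies under the tables: those at discontinuation for failure remain.
- That the two distortions cannot be disentangled: they fall on different endpoints, which section 6.2.3 also reports separately. They mix only in the combined count. What cannot be recovered is an endoscopy that was never done.

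**Conclusion.** The point holds in two limited parts.

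1. As written, dysphagia alone can be counted as symptomatic relapse. This can inflate the surgical arm's symptomatic relapse, point and periodic, and the combined endoscopic/symptomatic count. The protocol does not allow the size to be computed. On the assumed rates shown, the spurious difference runs from 0 to about 12 points, and it is zero if moderate-severe dysphagia is equally common in both arms.

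2. The tables and the text of section 3.1 contradict each other on the trigger for extra-visit endoscopy. This is an inconsistency, not an established bias. If sites follow the tables, endoscopic relapse between scheduled endoscopies could be under-detected in the surgical arm, for relapses managed without withdrawal.

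The primary log-rank analysis and endoscopic relapse at scheduled endoscopies are not affected. The change is worth making because recurrence prevalence is a stated objective and the repair is small, but the trial's main conclusion does not depend on it.

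**What to change.** - In section 4.3.4.2, define symptomatic relapse for the between-arm comparison by moderate-severe heartburn and/or acid regurgitation, and report dysphagia on its own line by arm and visit. Label this as the analysis definition, because section 3.1 also uses symptomatic relapse as a clinical trigger. Use the same definition in the combined count of section 6.2.3.
- Reconcile Table 1 footnote 15 and Table 2 footnote f with section 3.1, so that sites have one statement of when an extra-visit endoscopy is done. Which rule applies is for the sponsor and investigators to decide.
- Beside between-visit endoscopic relapse, show the number of unscheduled endoscopies in each arm, so that a reader can see whether both arms were examined equally often.

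The cost is one sentence, two footnotes, one extra line for dysphagia and one row of counts. Symptoms are already recorded separately, so no new data are needed. The drawback is that the comparison departs from the protocol's own list of GERD symptoms. Showing the count with dysphagia included as a supplement would keep that link.
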